9.2.2 Analysis of Remission Rate on the PARS

Remission rate on the PARS at acute treatment endpoint (Week 8) is defined as PARS severity score for GAD <8 (using 6 PARS items: 2, 3, 4, 5, 6, and 7). The analysis of remission rate will be conducted using the same methodology as the response rate on the PARS.

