8.3 Selection of Study Population

8.3.1 Number of Planned Subjects

A total of approximately 430 subjects will be screened and approximately 256 subjects (128 per treatment arm) are planned to be randomized in approximately 40 centers in the United States. It is assumed that approximately 115 subjects per treatment arm will be evaluable (ie, have at least one postbaseline assessment).

A blinded interim analysis will be conducted when 75% of randomized subjects have either completed or discontinued the study in order to check the assumptions in the sample size calculation. Based on this, the sample size may be increased to ensure an adequate power due to variance assumption deviation as well as increased variance due to COVID-19 remote visits. However, due to the difficulties in recruiting pediatric

CONFIDENTIAL

subjects with GAD, the number of subjects in each treatment arm will be capped at 160 (see [Section 11.8](#)).

Re-screening of subjects who do not meet the entry criteria is not allowed, except for the reasons outlined in [Section 8.3.4](#). A subject can only be re-screened once.

The statistical considerations on which the sample size is based are provided in [Section 11.9](#).

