11.5.1.2 Secondary Efficacy Parameters

Inferential testing for the secondary endpoints will be reported with nominal p-values. No adjustments for multiplicity will be made. All confidence intervals will be 2-sided 95% confidence intervals, unless stated otherwise.

The secondary efficacy endpoints are as follows:

- Response rate on the PARS at acute treatment endpoint (Week 8)
 - Response is defined as a 50% improvement on the PARS severity score for GAD.
- Remission rate on the PARS at acute treatment endpoint (Week 8)
 - Remission is defined as PARS severity score for GAD ≤ 8 (using 6 PARS items: 2, 3, 4, 5, 6, and 7)
- Change on the CGI-S from baseline to acute treatment endpoint (Week 8)

CONFIDENTIAL

- Remission rate on CGI-S at acute treatment endpoint (Week 8).
Remission rate is defined as the percentage of subjects having a CGI-S score ≤ 2 at endpoint.
- Change on the CGAS from baseline to acute treatment endpoint (Week 8)
 - Remission rate on the CGAS at acute treatment endpoint (Week 8).
Functional remission is defined as CGAS > 70 .
- COVID-19 impact assessment score at each visit.

The response rate of the PARS will be analyzed using a repeated measures model for categorical outcomes. Modeling will be completed using a categorical MMRM (MMRM-CAT) approach, in which a pseudo-likelihood-based repeated measures analysis will be used and implemented in SAS procedure GLIMMIX. A binary distribution with logit link will be used for the dependent variable. Classification variables for treatment, age group, sex, visit (as a categorical variable), treatment-by-age group interaction, treatment-by-sex interaction, treatment-by-visit interaction, and treatment-by-age group-by-sex interaction, and baseline score as a covariate will be considered in the modeling.

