9.2 SECONDARY EFFICACY PARAMETERS

The secondary efficacy endpoints are as follows:

- Response rate on the PARS at acute treatment endpoint (Week 8)
- Remission rate on the PARS at acute treatment endpoint (Week 8)
- Change on the CGI-S from baseline to acute treatment endpoint (Week 8)
- Remission rate on CGI-S at acute treatment endpoint (Week 8)
- Change on the CGAS from baseline to acute treatment endpoint (Week 8)
- Remission rate on the CGAS at acute treatment endpoint (Week 8)
- COVID-19 impact assessment score at each visit.

Page 27 of 53

Inferential testing for the secondary endpoints will be reported with nominal p-values. No adjustments for multiplicity will be made. All confidence intervals will be 2-sided 95% confidence intervals, unless stated otherwise

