9.2.3 Summary of PARS Severity Score at each Visit

Observed values and change from baseline in the PARS severity score will be summarized by treatment at each visit.

9.2.4 Analysis of Change on the CGI-S from Baseline and Remission Rate of CGI-S

The CGI-S is a 7-point scale developed for use in clinical trials to provide an assessment of the clinician's view of the patient's global functioning. The change from baseline in CGI-S will be analyzed using the same methodology described for the primary efficacy parameter. The subject-level CGI-S score will be listed.

Page 28 of 53

The remission rate of CGI-S at acute treatment endpoint (Week 8) is defined as percentage of subjects having a CGI-S score ≤2 at endpoint. The remission rate will be analyzed using the same methodology described for the analysis of the response rate on the PARS.

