13.0 BLINDED INTERIM ANALYSIS

A blinded interim analysis will be conducted when approximately 75% of randomized subjects have either completed the study or discontinued from the study. The blinded interim analysis is to obtain an estimate of the pooled standard deviation of the change from baseline in the PARS score to Week 8 of the double-blind acute treatment period. The sample size will be re-estimated using simulation in the same manner as the original sample size as described in Section 14 using the estimated pooled standard deviation and dropout rate from the blinded interim analysis. If the estimated pooled standard deviation is larger than the assumed pooled standard deviation due to assumption deviation as well as COVID-19 remote visits or dropout rate is increased, the sample size in placebo and escitalopram treatment groups may be increased to ensure an adequate power. However, due to the difficulties in recruiting pediatric subjects with GAD, the number of subjects in each treatment arm will be capped at 160.

As the sample size re-estimation requires only the pooled standard deviation and dropout rate to be updated, all data and personnel will remain blinded for the interim analysis. Randomization code will not be released for the sample size re-estimation. There are no potential unblinding issues in the sample size re-estimation. As this is a blinded re-estimation, there is no impact on the overall Type I error rate of the study.

SAP SCT-MD-60 Allergan

Page 40 of 53

14.0 DETERMINATION OF SAMPLE SIZE

The sample size estimate was constructed using a simulation approach as described in Lu K. (2012).

The primary efficacy parameter is the change from baseline to Week 8 of the double-blind acute treatment period in PARS total score. To detect an effect size (treatment group difference of 2.30 units relative to pooled standard deviation of 5.79) of 0.39, a sample size of 128 subjects in the escitalopram treatment group and 128 subjects in the placebo group will provide 85% power based on an MMRM model using simulation method. The simulation assumed a correlation of 0.7 between the repeated measures, and a common dropout rate of 14%, based on historical data of escitalopram in pediatric subjects.

SAP SCT-MD-60 Allergan

Page 41 of 53

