16.9 CHARACTER VALUES OF CLINICAL LABORATORY PARAMETERS

If the reported value of a clinical laboratory parameter cannot be used in a statistical summary table because, for example, a character string is reported for a parameter of the numeric type, a coded value must be appropriately determined for use in the statistical analyses. The actual values, as reported in the database will be presented in the data listings.

Table 16.9–1 shows examples of how some possible laboratory results should be coded for analysis.

Page 49 of 53

Table 16.9–1. Examples of Coding Special Character Values for Clinical Laboratory Parameters

Laboratory Test, SI Unit	Possible Laboratory Results	Coded Value for Analysis
CHEMISTRY		 
ALT, U/L	< 5	5
AST, U/L	< 5	5
Bilirubin, total, μmol/L	< 2	2
URINALYSIS		
	< 2.775, Negative	0
	[2.775, 5.55)	1+
C1	[5.55, 13.875)	2+
Glucose, mmol/L	[13.875, 27.75)	3+
	[27.75, 55.5)	4+
	≥ 55.5	5+
141/T	$> 0.444, \ge 0.444, >0$, Trace	Positive
ketones, mmol/L	≤ 0, Negative	Negative
pH	> 8.0, ≥ 8.0	8.0
	≥ 8.5	8.5
	< 0, Negative	Negative
	[0, 0.15), Trace	0
Dustain a/I	[0.15, 0.3)	1+
Protein, g/L	[0.30, 1.0)	2+
	[1.0, 5.0)	3+
	>= 5.0	4+

ALT = alanine aminotransferase; AST = aspartate aminotransferase; SI = Le Système International d'Unités (International System of Units).

SAP SCT-MD-60 Allergan

Page 50 of 53

17.0 CHANGES TO ANALYSES SPECIFIED IN PROTOCOL

Only the following changes have been made to the protocol version 3.0: 30 Jun 2020.

Per protocol section 11.3, demographic parameters to be summarized include weight z-score and height z-score. However, these will be listed but not summarized.

No other changes have been made to the analyses specified in the protocol.

Page 51 of 53

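### SAP Section 9.2.2 sets PARS remission at a 6-item score below 8, the protocol sets it at 8 or below, and SAP Section 17.0 does not declare the difference

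*SAP*

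**What the plan says.** The protocol defines PARS remission twice, in the Synopsis and in Section 11.5.1.2, with the same cut-off each time: "Remission is defined as PARS severity score for GAD ≤ 8 (using 6 PARS items: 2, 3, 4, 5, 6, and 7").

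SAP Section 9.2.2 covers the same endpoint at the same visit with the same six items, but there remission "is defined as PARS severity score for GAD <8 (using 6 PARS items: 2, 3, 4, 5, 6, and 7").

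SAP Section 17.0, which lists departures from the protocol, opens with "Only the following changes have been made to the protocol version 3.0: 30 Jun 2020". Its only entry is that weight and height z-scores will be listed and not summarized. It closes with "No other changes have been made to the analyses specified in the protocol".

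PARS remission is one of seven secondary endpoints listed in SAP Section 9.2. For these, "Inferential testing for the secondary endpoints will be reported with nominal p-values", without multiplicity adjustment.

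**The concern.** The items, visit and endpoint agree and only the inequality differs, so the two definitions disagree for exactly one score, a 6-item sum of 8. The SAP measures itself against protocol version 3.0, which is the current protocol, so this is not a comparison with superseded text. The SAP's definition and its statement that nothing else changed cannot both be right.

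The SAP is the document that programmers work from. Someone coding Section 9.2.2 literally would drop every subject scoring 8 from the remitters, and the reported endpoint would depart from the protocol without notice. At stake are the reported remission rates in both arms and, to a smaller degree, the treatment contrast. If the conflict is still open at unblinding, the choice between two cut-offs could be made with the results in view.

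**Working it through.** **Comparing the definitions**

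| Source | Items | Visit | Cut-off | Score of 8 |
|---|---|---|---|---|
| Protocol, Synopsis and Section 11.5.1.2 | 2, 3, 4, 5, 6, 7 | Week 8 | ≤ 8 | remitter |
| SAP Section 9.2.2 | 2, 3, 4, 5, 6, 7 | Week 8 | < 8 | non-remitter |

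Scores of 7 or less, and of 9 or more, are classified the same way under both. No power, alpha or sample-size figure in the plan uses this cut-off, so there is no stated figure to reproduce.

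**How many subjects could score exactly 8**

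The documents do not give the Week 8 distribution, so what follows is an illustration.

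Inputs from the documents:
- Planned difference and SD (SAP Section 14.0): "treatment group difference of 2.30 units relative to pooled standard deviation of 5.79". Both belong to the primary change score, which uses five items; they are borrowed here for a six-item absolute score.
- Evaluable subjects (Protocol Section 8.3.1): "approximately 115 subjects per treatment arm will be evaluable".

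Assumptions: whole-number, approximately normal Week 8 scores; placebo mean m from 8 to 14; escitalopram mean m − 2.30; SD s of 5, 5.79 or 7 in both arms.

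1. Share scoring exactly 8: P(8) = Φ((8.5 − m)/s) − Φ((7.5 − m)/s), with the arm's own mean for m.
 - Smallest value, mean 14 and s = 5: 0.0389; × 115 = 4.5 subjects.
 - Largest value, mean 8 and s = 5: 0.0797; × 115 = 9.2 subjects.

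2. Change in the between-arm difference (escitalopram minus placebo) on moving from ≤ 8 to < 8. Each arm loses its own P(8), so the change is P(8 | placebo) − P(8 | escitalopram).
 - Placebo mean 14, s = 5: 0.0389 − 0.0606 = −0.022.
 - Placebo mean 8, s = 5: 0.0797 − 0.0717 = +0.008.

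3. Worked example, placebo mean 12, escitalopram mean 12 − 2.30 = 9.70, s = 5.79:

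| Cut-off | Escitalopram | Placebo | Difference | Odds ratio |
|---|---|---|---|---|
| ≤ 8 | Φ((8.5 − 9.7)/5.79) = 41.8% | Φ((8.5 − 12)/5.79) = 27.3% | 14.5 points | 1.91 |
| < 8 | Φ((7.5 − 9.7)/5.79) = 35.2% | Φ((7.5 − 12)/5.79) = 21.9% | 13.3 points | 1.94 |

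The odds ratio is [p₁/(1 − p₁)] / [p₀/(1 − p₀)], with p₁ for escitalopram and p₀ for placebo. The rates fall by 6.6 and 5.4 points, while the odds ratio hardly moves.

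**Sensitivity of the illustration.** With means of 8 to 16 and SDs of 4 to 5.79, the share scoring exactly 8 runs from 1.4% to 9.9%.

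**The case against.** The strongest objection is that the point rests on one character in text extracted from a PDF. Symbols elsewhere in the extracted SAP are irregular: some superscripts in the visit schedules are garbled, and in Section 10.2 the second total bilirubin threshold has no comparison sign. A ≤ that lost its bar is possible. This stands as a caveat. Against it, the CGI-S remission rule in SAP Section 9.2.4 keeps its sign ("having a CGI-S score ≤2 at endpoint"), which makes a lost bar less likely but does not exclude it.

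A second objection is that the intended reading is clear: the protocol says ≤ 8 twice and the SAP denies any other change, so < 8 is probably a slip. That may well be so, but a probable slip in the document used for programming still has to be corrected.

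A third is that the consequence is small. This is largely right. The endpoint is one of seven secondaries with nominal p-values, and in the example the odds ratio, the scale of the planned logit model, barely changes.

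The illustration also has real limits:
- The placebo means have no source in the documents.
- A normal curve at mean 8 and SD 7 puts about 11% of its mass on scores below zero (below −0.5), so the low end of the range is rough.
- The 115 evaluable subjects need only one post-baseline assessment. With the planned 14% dropout, 128 × 0.86 ≈ 110 per arm would have a Week 8 score. The count is then still about 4 to 9.

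**Conclusion.** The concern holds. As the text stands, PARS remission has two definitions that disagree for a score of 8, and the SAP's list of changes does not account for it. The documents do not show whether < 8 is a slip or an intended change.

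Under the stated assumptions, about 4% to 8% of each arm would change status, and the between-arm difference would move by about two percentage points at most. The size rests on assumed distributions; the conflict at a score of 8 does not. The primary analysis, alpha, power and the blinded sample-size re-estimation are unaffected. The remaining uncertainty is whether the sign was read correctly from the PDF. If the source shows ≤ 8, the point falls away.

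**What to change.** First, check the sign in the source PDF of the SAP. If it reads ≤ 8, nothing more is needed.

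If it reads < 8, change the cut-off in SAP Section 9.2.2 to ≤ 8 on items 2, 3, 4, 5, 6 and 7, matching the protocol. If the stricter cut-off is intended, declare and justify it in SAP Section 17.0 before unblinding.

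The cost is one character, or one sentence. Data collection and design do not change.

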9.2.3 Summary of PARS Severity Score at each Visit

Observed values and change from baseline in the PARS severity score will be summarized by treatment at each visit.

9.2.4 Analysis of Change on the CGI-S from Baseline and Remission Rate of CGI-S

The CGI-S is a 7-point scale developed for use in clinical trials to provide an assessment of the clinician's view of the patient's global functioning. The change from baseline in CGI-S will be analyzed using the same methodology described for the primary efficacy parameter. The subject-level CGI-S score will be listed.

Page 28 of 53

The remission rate of CGI-S at acute treatment endpoint (Week 8) is defined as percentage of subjects having a CGI-S score ≤2 at endpoint. The remission rate will be analyzed using the same methodology described for the analysis of the response rate on the PARS.

9.2.5 Summary of CGI-S Score at each Visit

Observed values and change from baseline in the CGI-S score will be summarized by treatment at each visit.

9.2.6 Analysis of Change on the CGAS from Baseline and Remission Rate of CGAS

The CGAS is a 100-point scale range from 1 to 100 used as a measure of global functioning and impairment. The change in the CGAS will be analyzed using the same methodology described for the primary efficacy parameter.

Remission rate on the CGAS at acute treatment endpoint (Week 8) is defined as CGAS >70. The analysis of the remission rate for the CGAS will use the same methodology described for the analysis of the response rate on the PARS.

9.2.7 Summary of CGAS Score at each Visit

Observed values and change from baseline in the CGAS score will be summarized by treatment at each visit.

9.2.8 Analysis of COVID-19 impact assessment score

The global COVID-19 impact assessment will be used to evaluate the impact of the coronavirus disease pandemic on the severity of the subject's GAD during the last 1 week. The rating will include scores from 0 (not applicable, subject not enrolled in the trial during the pandemic) to 7 (extreme impact). Raters will also evaluate whether the impact was an improvement or worsening of the subject's GAD.

Subjects with scores from 4 (moderate impact) to 7 (extreme impact) at any visit other than the Screening Visit will be considered to have been significantly impacted, regardless of the direction of impact.

Number and percentage of subjects with each score on the global COVID-19 impact assessment will be summarized descriptively at each visit by treatment group for the mITT population, including subjects that were significantly impacted. For each score from 2 to 7, the number and percentage of subjects who improved or worsened will also be summarized.

Page 29 of 53

Page 30 of 53

10.0 SAFETY ANALYSES

The safety analysis will be performed for the double-blind acute treatment period and the double-blind down-taper period separately, using the Safety Population unless stated otherwise.

The safety parameters include adverse events (AEs), clinical laboratory parameters, vital signs, electrocardiographic (ECG) parameters, and suicide risk assessment using the Columbia-Suicide Severity Rating Scale (C-SSRS). For each safety parameter, the last non-missing safety assessment before the first dose of double-blind investigational product will be used as baseline. Continuous variables will be summarized by number of subjects and mean, SD, median, minimum, and maximum values. Categorical variables will be summarized by number and percentage of subjects.

Safety data collected outside of planned visit windows but within allowance limits (up to 1 week late for Visits 7 and 8) will be included in the summary tables. Safety data collected outside of planned visit windows and outside of the allowance limits (>1 week to 6 weeks late for Visits 7 and 8) will be listed, but will not be included in the summary tables. Subgroup analyses may be performed to assess the impact of COVID-19 on the safety analyses; details are listed in each safety section.

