The coronavirus disease 2019 (COVID-19) pandemic (and any other naming conventions used) developed after this study began and this protocol has been amended to account for study procedures that need to be modified in association with adhering to local safety guidelines or regulations.

[figure not shown]
During the COVID-19 pandemic, remote study visits, in which data are collected via telephone or videoconference, are possible but not preferred. Nearly all scheduled safety assessments, with exception of the Columbia-Suicide Severity Rating Scale (C-SSRS), are not possible by remote visit and must be collected in person via clinic visits. To

CONFIDENTIAL

accommodate changes sites may need to implement during the pandemic, [Section 8.1.2](#) outlines the conduct of study assessments during in-clinic visits, which is the preferred method of conducting the study, while study assessments for remote visits are included in [Section 8.1.3](#).

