8.1.3 Schedule of Assessments that Can Be Done Remotely

Period	Double-blind Acute Treatment Period						Double-blind Down Taper Period	Follow-up
Visit	2	3	4	5	6	7/ET ^a	8 ^b	Telephone Contact
Day/Week	Baseline Day 1	Week 1 ^c	Week 2 ^c	Week 4 ^c	Week 6 ^c	Week 8/ET ^c	Week 9 ^c	Week 10 ^c
Inclusion/Exclusion Criteria	X							
Randomization	X							
C-SSRS	X	X	X	X	X	X	X	
CGAS	X	X	X	X	X	X		
PARS	X		X			X		
CGI-S	X		X			X		
Global COVID-19 impact assessment ^d	X	X	X	X	X	X	X	
Evaluate for Dose Escalation ^e			X	X				
Dispense Study Drug ^f	X ^g	X	X	X	X	X		
Study Drug Accountability		X	X	X	X	X	X	
Adverse Events	◀-----►-----►							
Concomitant Medications	◀-----►-----►							

Abbreviations: CGAS = Children's Global Assessment Scale; CGI-S = Clinical Global Assessment of Severity; COVID-19 = coronavirus disease 2019; C-SSRS = Columbia-Suicide Severity Rating Scale; ET = End of Treatment; PARS = Pediatric Anxiety Rating Scale; PK = pharmacokinetic.

Notes for Remote Study Visits:

- The Baseline Visit can be remote but it is not preferred. For all female subjects of childbearing potential, the Baseline Visit must take place as an in-clinic visit with all assessments outlined in [Section 8.1.2](#).
- Subject data are collected via telephone or telehealth video calls using a technology provider (see [Appendix 17.3](#)). Sites should remain consistent with either methods (video or telephone) for each subject.
- In-clinic safety and PK assessments missed due to remote visits may be collected per [Section 8.2.2.1, Table 1](#).

^a End of Treatment or Early Withdrawal.

^b If a site becomes aware of any adverse events after study completion (occurring outside of a defined study visit, including any contact up to 30 days after receiving the last dose of study drug), all adverse events reported by the patient or patient representative or observed or otherwise identified by the investigator or other study personnel must be documented.

^c Visit window ± 3 days.

^d To be completed last after all other study assessments.

^e Subjects who can tolerate the current dose of 10 mg/day may have a dose escalation to 20 mg/day at the investigator's discretion taking into account the CGI-S score.

^f For remote visits study drug will be sent to subjects via curbside (preferred) or courier.

^g In case of a remote Baseline Visit, subjects will receive and take their first dose of study drug via curbside (preferred) or they will receive it by courier and take it at home.

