9.3 Down Taper Period

9.3.1 Week 9 (Visit 8)

The Week 9 Visit (Visit 8) will take place 9 weeks \pm 3 days after the Baseline Visit. The following procedures will be performed at Visit 8:

- Perform an accountability check on any remaining study drug as well as empty study drug bottles.
- Record any AEs that have occurred since the last visit and any changes in concomitant medications.
- Complete C-SSRS.
- Record vital signs (blood pressure, pulse rate, temperature, and respiration rate).
- Schedule a follow-up telephone contact in 1 week's time.

CONFIDENTIAL

Refer to [Section 8.1.3](#) for assessments and to [Table 1](#) for assessment windows if Visit 8 is done remotely.

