To examine the consistency of the primary efficacy results across study centers, the treatment differences versus placebo treatment groups (mean \pm SE) in the change from baseline to Week 8 in PARS severity score, both OC and LOCF, will be graphed by pooled study center.

The comparison of escitalopram vs. placebo will be performed to assess study assay sensitivity.

To assess the impact of COVID-19 on the primary efficacy parameter:

- The primary analysis will be repeated for subjects that were not significantly impacted by COVID-19 (Global COVID-19 Impact Assessment score of 4 or higher, regardless of direction of impact; see section 9.2.5).
- A sensitivity analysis will be conducted by treating remote visits as missing, and analyzing the remaining data using the primary MMRM model.
- A sensitivity analysis will be conducted by repeating the primary analysis and adding the following to the model: an indicator of whether data was collected before or on and after the start of the pandemic (17 March 2020) and the indicator by treatment interaction.
- A subgroup analysis will be conducted by repeating the primary analysis for randomized patients before or on and after the start of the COVID-19 pandemic (17 March 2020).

The subject-level PARS scores will be listed

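### The SAP's rule for 'significantly impacted by COVID-19' uses a Week 9 rating scheduled only at remote visits and does not say how to class unrated subjects, so the subset for one supportive re-run of the primary analysis is not properly defined

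*SAP*

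**What the plan says.** The flag is defined in SAP 9.2.8: a subject with a score of 4 to 7 "at any visit other than the Screening Visit will be considered to have been significantly impacted", whichever way the impact went. Score 0 is reserved for subjects not enrolled during the pandemic. The section gives no rule for a missing rating.

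The flag is used in SAP 9.1.2: "The primary analysis will be repeated for subjects that were not significantly impacted by COVID-19". The parenthesis that follows puts the threshold on the wrong group, since it reads "subjects that were not significantly impacted by COVID-19 (Global COVID-19 Impact Assessment score of 4 or higher". It then refers to SAP 9.2.5, which is the by-visit CGI-S summary; the definition is in 9.2.8.

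The two visit schedules differ at Week 9. In the remote schedule (Protocol 8.1.3, SAP 3.3) the row "Global COVID-19 impact assessment" is marked from Visit 2 through Visit 8 (Week 9). In the clinic schedule (SAP 3.2) it is marked for Visits 1 to 7/ET only. In Protocol 9.3.1 the list introduced by "The following procedures will be performed at Visit 8" contains no COVID-19 rating.

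On timing, Protocol 8.1 says that the pandemic "developed after this study began". SAP 9.1.2 dates its start at 17 March 2020. The protocol's amendment summary shows that the rating was added in Version 3.0, dated 30 June 2020, which is the version the SAP works from.

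**The concern.** The re-run is meant to show the treatment effect with pandemic-affected subjects removed. It can do so only if membership depends on how much a subject was affected. As written, membership also depends on which ratings happen to exist.

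A subject whose Week 9 visit was remote has one more chance of being removed than a clinic subject with the same experience. That extra rating asks about the week after the primary score was taken. At the other end, a subject seen in spring 2020, before the rating existed, cannot reach 4 and so stays in the 'not impacted' group. The mITT definition (SAP 5.4) requires PARS scores but no COVID-19 rating, so nothing upstream removes that subject.

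What is at stake is the meaning of one robustness check. It is the only COVID-19 analysis in SAP 9.1.2 built on rated individual impact; the others use visit mode or calendar date.

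**Working it through.** **1. The plan's own figure.** The plan gives no number for this flag. The one stated figure that bears on the re-run is the 85% power in SAP 14.0, and the point does not depend on it. It reproduces approximately. Inputs: difference 2.30, SD 5.79, correlation 0.7, 14% dropout, 128 per arm. With PARS measured post-baseline at Weeks 2 and 8, the variance of the Week 8 difference is 2 × 5.79² × [(1 − 0.7²)/n8 + 0.7²/n2], where n8 = 128 × 0.86 = 110 and n2 lies between 110 and 128. Power is 83.8% to 86.3%.

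**2. Ratings that can trigger the flag, by path** (Screening excluded, as SAP 9.2.8 says):
- Completer seen in clinic: Visits 2 to 7, 6 ratings.
- Completer with a remote Week 9 visit: Visits 2 to 8, 7 ratings.
- Early withdrawal: as few as 2 (Baseline and ET).
- Subject who finished Week 8 before Version 3.0 was in use: 0, unless back-filled.

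**3. Dates.**
- 17 March to 30 June 2020: 14 + 30 + 31 + 30 = 105 days.
- Week 8 falls 56 days after Baseline. Week 8 on 17 March means randomization on about 21 January 2020. Week 8 on 30 June means randomization on about 5 May 2020.
- Randomized before about 21 January: all Baseline-to-Week 8 visits precede 17 March, so 'not impacted' is correct.
- Randomized from 21 January to 5 May (105 days, 15 weeks): some visits in the pandemic period and none after 30 June. These are the wholly unrated subjects. The window ends later if sites took up Version 3.0 after its date.
- Randomized from 5 May to 30 June: at least a Week 8 rating is possible, so they are partly rated.

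The documents give no recruitment rate. Purely as an illustration, 2 to 3 randomizations a week would give 30 to 45 wholly unrated subjects (12% to 18% of 256) if recruitment never paused. If it stopped on 17 March, the window is 8 weeks and the count 16 to 24 (6% to 9%).

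**4. How far the number of ratings alone moves the flag.** The documents give no rate of scores of 4 or more. Assume a chance of 5% to 20% per rating and a within-subject latent correlation of 0 to 0.8. With independence the chance of being flagged is 1 − (1 − p)^k; for p = 10%, 1 − 0.9⁶ = 46.9% and 1 − 0.9⁷ = 52.2%. With correlation it was simulated (latent normal, 400,000 draws).

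| Ratings | p = 10%, correlation 0.5 | Full assumed range |
|---|---|---|
| 0 | 0% | 0% |
| 2 | 17% | 7.5% to 36% |
| 4 | 26% | 11% to 59% |
| 6 | 32% | 13% to 74% |
| 7 | 35% | 13% to 79% |

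The step from 6 to 7 ratings, which is the remote Week 9 effect, runs from 13.3 − 12.6 = 0.7 points to 79.0 − 73.7 = 5.3 points. It applies only to subjects whose Week 9 visit was remote.

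**The case against.** The best reply is that the SAP is silent, not wrong. It never says that unrated subjects count as not impacted. Score 0 suggests that entries for earlier subjects were contemplated, since someone rated prospectively after the amendment could hardly earn it, so back-filling cannot be excluded. This stands: the default follows from taking the complement of the definition and is not a written rule. But score 0 does not fit a subject seen in April 2020, and the rating asks about the last week only, which makes later completion difficult.

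A reader might infer that a large share of the trial is misclassified, by taking every subject randomized from 21 January to 30 June (161 days, 23 weeks) at 2 to 3 a week, or 46 to 69 subjects. The documents do not support that. The rate is not in them, the 23 weeks mix partly rated with wholly unrated subjects, and Protocol 8.3.4 refers to a recruitment hold.

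A reader might also infer that the primary result is biased. It is not touched. The three other COVID-19 analyses in SAP 9.1.2 (remote visits set to missing, a collection-date indicator with its treatment interaction, and a subgroup by randomization date) do not use the flag. The trial is double-blind, and gaps caused by the calendar should fall alike in both arms.

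Finally, the Week 9 rating matters only if that visit was remote, scored 4 or more, and no earlier rating did. The mark in the remote schedule may be a slip. That limits its size but does not remove the need to exclude a post-endpoint rating from the rule.

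**Conclusion.** The concern holds as a minor one. The definition in SAP 9.2.8 lets a rating taken after the endpoint, and scheduled only at remote visits, remove a subject from the re-run. It also leaves open where unrated pandemic-period subjects go; read literally, they stay in. In SAP 9.1.2 the parenthesis describes the wrong group and the cross-reference leads to the wrong section.

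The number affected cannot be determined from the documents. The dates bound the wholly unrated subjects to a 15-week randomization window, assuming that the rating came into use on 30 June 2020 and was not back-filled. The recruitment hold may shrink that number and late uptake may enlarge it. The Week 9 effect is probably small. Only this supportive analysis is affected; the primary test and its error rate are not.

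**What to change.** In SAP 9.2.8:
- Base the flag on ratings from Baseline through Visit 7/ET.
- Class as 'not assessed' only subjects who have at least one Baseline-to-Week 8 visit on or after 17 March 2020 and no rating at any such visit. Report their number by arm.
- Run the 'not significantly impacted' analysis without these subjects, then with them.
- Keep subjects who finished before 17 March 2020 as 'not impacted'. State that a single missed rating does not remove a subject; otherwise the fix would itself sort subjects by which ratings exist.

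In SAP 9.1.2, reword the parenthesis so that a score of 4 or higher defines the excluded subjects, and cite 9.2.8. Make these changes before unblinding, so that the subset is not chosen with results known.

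The cost is wording, one extra run and a somewhat smaller subset. With the variance formula above and all dropouts leaving after Week 2, power is 86.3% with nobody left out, 82.6% if 10% of each arm is left out and 78.0% if 20% is.
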